6.9 Final Follow-Up (1 Year \pm 90 Days)

All assessments are to be conducted in accordance with routine care at each participating hospital, the following data will be collected but is not limited to:

- Aneurysm occlusion grade
- Vital signs
- mRS
- Retreatment information
- Adverse event review
- Angiography*

*Angiography will be performed per institutional standard of care. DSA, CTA, or MRA are accepted for imaging modality. Images will be sent to an Imaging Core Laboratory to make a final determination on aneurysm occlusion rate. If both DSA and MRA are available, then both imaging modalities should be submitted for Core Laboratory review.

Table 2: Schedule of Assessments

ACTIVITY	SCREENING & BASELINE	PROCEDURE	7-DAY AND/OR DISCHARGE	FINAL FOLLOW-UP (1 YEAR ± 90 DAYS)
Written Informed Consent	X ¹			
Demographics	X			
Medical History	X			
Vitals	X		X	X
mRS	X ²		X	X
Hunt & Hess	X ³			
Procedure		X ⁴		
Occlusion Grading		X		X ^{4,5,6}
Adverse Event Review		X	X	X

¹ For sites in North America, patients who have had an index procedure with SMART Coils and all inclusion/exclusion confirmed, may be consented up to 2 days post procedure but prior to discharge

² Baseline mRS is based on subject status prior to the index procedure

³ For patients presenting with SAH

⁴ Imaging should be uploaded into Image Management System within 14 days

⁵ Occlusion Grading and other datapoints will be collected if retreatment occurs prior to study exit

⁶ If both DSA and MRA are performed as part of standard of care follow-up, then both imaging modalities should be submitted for Core Laboratory review

7. Investigator Responsibilities

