7.5 Image Upload

Images from Immediate Post Procedure and Final Follow-Up visit may be uploaded to an image management system for Core Lab review. Instructions for image collection and upload will be provided. Study staff shall ensure that no images contain any personally identifying information about the subject or study site (e.g. Physician name, Institution name, patient name, etc.).

Sites will be provided with instructions for how images should be collected and submitted within 14 days of the acquisition of the required imaging. If the site is unable to provide the images within this time frame, the appropriate Sponsor contact should be notified.

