8.1 Primary Effectiveness Analysis

For the primary effectiveness endpoint, frequency counts, percentages, and two-sided 95% Wald confidence intervals will be reported using the ITT population:

- **Adequate occlusion defined as Raymond-Roy Occlusion Class I and II at final follow-up:** The percentage of patients assessed as Raymond-Roy Class I or II out of patients who had a Raymond-Roy evaluation done (Class I, II, or III) at the time of final follow-up. Retreatments at final follow-up will be modelled as Raymond-Roy Class III.

The core lab data supersede the investigator-reported data in primary and secondary effectiveness analyses.

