8.2 Secondary Effectiveness Analysis

For the secondary effectiveness endpoints, frequency counts, percentages, and two-sided 95% Wald confidence intervals will be reported using the ITT population:

- **Immediate post-procedure occlusion rate:** The percentage distribution of patients assessed as each of Raymond-Roy Class I, Class II, and Class III out of patients who had a Raymond-Roy evaluation done (Class I, II, or III) at immediate post-procedure.
- **Retreatment rate at final follow-up:** The percentage of patients who had the target aneurysm retreated since the index procedure out of patients who have data on this question (Retreatment, No Retreatment) at the time of final follow-up. Staged procedures are not retreatments for the purposes of running all SURF study analyses.
- **Aneurysm Occlusion Raymond I post treatment:** The percentage of patients assessed as Raymond-Roy Class I out of patients who had a Raymond-Roy evaluation done (Class I, II, or III) at immediate post-procedure.
- **Aneurysm Occlusion Raymond I at final follow-up:** The percentage of patients assessed as Raymond-Roy Class I out of patients who had a Raymond-Roy evaluation done (Class I, II, or III) at the time of final follow-up. Retreatments at final follow-up will be modelled as Raymond-Roy Class III.
- **Aneurysm recanalization or progressive thrombosis from post procedure to final follow-up:** The percentage of patients who experienced a deterioration in Raymond-Roy Occlusion Grading (aneurysm recanalization; Class I becoming II or III, or Class II becoming III) or improvement in Raymond-Roy occlusion (progressive thrombosis; Class II becoming I, or Class III becoming I or II) out of patients who had a Raymond-Roy evaluation done at both time points. Retreatments at final follow-up will be modelled as aneurysm recanalization.

The effectiveness endpoints will be reported using only the Raymond-Roy Occlusion Grading Scale. However, frequency counts, percentages, and two-sided 95% Wald confidence intervals will also be provided for the Meyers Consensus Grading Scale Grades 0, 1, 2, 3, 4, and 5 at immediate post-procedure and final follow-up, using the ITT population and core lab data.

Aneurysm packing densities will be reported as the coil volume of all Penumbra and non-Penumbra coils implanted divided by the aneurysm volume as measured by the core lab, based on two-dimensional geometric modeling as the primary analysis and the ABC method as a supplemental analysis.

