8.3 Imaging Outcomes Analysis

DSA is the reference standard imaging modality for aneurysm assessment after coiling, but MRA imaging is safer for patients and less expensive. Therefore, an imaging outcomes analysis will assess how successfully MRA scans detect residual aneurysm blood flow at final follow-up as compared to DSA scans, based on sensitivity, specificity, and related summary measures.

For each of Raymond-Roy Class II to III (any residual flow), Class II (residual neck), and Class III (residual aneurysm) at the time of final follow-up, the following statistics will be reported using the ITT population and core lab data:

- **Sensitivity:** The proportion of true positives (patients belonging to each of the three Raymond-Roy groups above on DSA) that are correctly identified as such on MRA as well. The percentages of patients assessed as each of Raymond-Roy (1) Class II to III, (2) Class II, and (3) Class III on MRA and DSA out of patients with the same Raymond-Roy group assessed on DSA at the time of final follow-up will be computed.
- **Specificity:** The proportion of true negatives (patients not belonging to each of the three Raymond-Roy groups above on DSA) that are correctly identified as such on MRA as well. The percentages of patients assessed as each of Raymond-Roy (1) Class I, (2) Class I or Class III, and (3) Class I to II on MRA and DSA out of patients with the same Raymond-Roy group assessed on DSA at the time of final follow-up will be computed.
- **Positive likelihood ratio (LR):** Sensitivity divided by (1 - Specificity).
- **Negative likelihood ratio (LR):** (1 - Sensitivity) divided by Specificity.
- **Cohen's κ :** Summary measure of agreement between DSA and MRA in detecting each of Raymond-Roy Class II and III, Class II, and Class III.

As a secondary comparison, this analysis will be repeated using each of Meyers Consensus Grading Scale Grades 1 to 5 (any residual flow), Grade 1 (90% or greater aneurysm occlusion), Grade 2 (70-89% aneurysm occlusion), Grade 3 (50-69% aneurysm occlusion), Grade 4 (25-49% aneurysm occlusion), and Grade 5 (Less than 25% aneurysm occlusion).

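### The SAP's 'supersede' rule lets site-only grades into the Raymond-Roy occlusion endpoints, with no count of such reads and no core-lab-only analysis; the image-upload wording also conflicts

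*Combined protocol and SAP*

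**What the plan says.** **Which read counts.** SAP 8.1 defines the primary rate as Class I or II "out of patients who had a Raymond-Roy evaluation done (Class I, II, or III) at the time of final follow-up". It does not say whose evaluation. The only rule about readers is one of precedence: "The core lab data supersede the investigator-reported data in primary and secondary effectiveness analyses". The Raymond-Roy endpoints in SAP 8.2 use the same reader-neutral denominator.

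**Where only core-lab data are meant, the SAP says so.** The Meyers grades in 8.2 are reported "using the ITT population and core lab data". For the MRA-versus-DSA comparison in 8.3, "the following statistics will be reported using the ITT population and core lab data".

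**A site value exists.** Among the data that protocol 6.9 collects at one year is "Aneurysm occlusion grade", and protocol 6.7 lists the same item at the procedure.

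**The core lab's role.** Protocol 6.9 states: "Images will be sent to an Imaging Core Laboratory to make a final determination on aneurysm occlusion rate". Protocol 6.7 says the same for procedural imaging, and protocol 11.1 has the core lab review both time points.

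**Upload.** Protocol 7.5 opens with: "Images from Immediate Post Procedure and Final Follow-Up visit may be uploaded to an image management system for Core Lab review". Its next paragraph speaks of required imaging due within 14 days, and tells a site that cannot meet this to notify the sponsor. Table 2 footnote 4 uses 'should be'; 6.7 and 6.9 use 'will be'.

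**Missing data.** SAP Section 12 analyses data as observed, without imputation. Its sensitivity analyses are imputation from baseline scores, worst case and best case.

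**The concern.** A precedence rule settles what happens when both reads exist. It does not settle what happens when only the site read exists. Such a patient has a Raymond-Roy evaluation and has available data, so a programmer following 8.1 and Section 12 as written would include the site grade.

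Four things follow.

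- The primary rate may mix independent and site reads in unknown proportion. No table shows that proportion, so a reader of the results could not detect it.
- A site-only patient counts as observed, so the worst-case and best-case analyses in Section 12 never touch that patient.
- Recanalization or progressive thrombosis needs a grade at two time points, but nothing requires the same reader at both. A site grade at one and a core-lab grade at the other would record reader disagreement as a change in the aneurysm.
- A missing upload is hard to see in the study records, because protocol 7.6.4 limits reportable deviations to eligibility and consent.

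The study is single-arm, and SAP 10.3 notes that there is no CEC and that adverse events rest on site assessment. The core lab is the independent assessor the plan provides for effectiveness, so its role should be secured in the analysis rules.

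**Working it through.** **1. The plan's own figure.** Inputs from SAP Section 2: 800 enrolled, 10% attrition, 641/720 adequate occlusion, two-sided 95% Wald interval.

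- 800 × 0.90 = 720.
- p = 641/720 = 0.8903.
- Half-width = 1.96 × √(p(1 − p)/720) = 2.28 points.
- Interval 86.74% to 91.31%. This reproduces the stated 87% to 91%.

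**2. Possible shift from mixing readers.** Let f be the share of evaluated patients with a site read only, and d the site-minus-core-lab difference in the adequate-occlusion rate. Shift = f × d. Neither f nor d is in the documents; the values below are assumptions, and d is taken as positive only for illustration.

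| f | d (points) | Shift (points) |
|---|---|---|
| 10% | 5 | 0.5 |
| 10% | 10 | 1.0 |
| 20% | 5 | 1.0 |
| 20% | 8 | 1.6 |
| 30% | 8 | 2.4 |
| 30% | 10 | 3.0 |

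The shift equals the half-width when f = 2.28/d: about 46% at d = 5, 29% at d = 8 and 23% at d = 10. With f at or below 10% it is at most 1 point over this range. A negative d would give shifts of the same size downwards.

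**3. Precision if only core-lab reads are used.** Half-width = 1.96 × √(0.89 × 0.11/n).

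- n = 720 × 0.80 = 576: 2.56 points.
- n = 720 × 0.70 = 504: 2.73 points.
- The half-width reaches 3 points at n = 1.96² × 0.0979/0.03² ≈ 418 reads.
- At 320/360 it is 3.25 points, inside the ±3.5% that the SAP gives for that row.

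**4. What Section 12 would cover.** Take f = 20%, so 720 − 576 = 144 site-only patients, and the same 89% rate in both groups.

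- Site grades counted as observed: worst case imputes failure for 800 − 720 = 80 patients, giving 641/800 = 80.1%.
- Core-lab reads only: worst case imputes failure for 80 + 144 = 224 patients. With 513 successes among 576 (0.89 × 576 ≈ 513), this gives 513/800 = 64.1%.

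Under the first handling, the sensitivity analyses say nothing about the 144. This calculation ignores retreated patients, who would stay failures either way.

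**The case against.** The strongest reply is that protocol 6.7 and 6.9 already give the core lab the final determination, that 11.1 has it review both time points with the sponsor tracking images received, and that a Core Lab Charter, not among the documents, may settle missing reads. The analyses are also descriptive (protocol 10.1), with no test or threshold for this endpoint, so no success decision turns on a shift of a point or so. All of this stands and limits the consequence. It does not close the gap, because the SAP defines the endpoint and says nothing on site-only grades.

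A reader might infer four stronger things that the documents do not support.

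- *That the SAP instructs site grades to fill in.* No sentence says so. It is the natural reading of the denominator, the precedence rule and the contrast with 8.2 and 8.3.
- *That upload is optional and sites choose what the core lab sees.* This rests on one sentence, that images "may be uploaded to an image management system for Core Lab review". Protocol 6.7, 6.9, Table 2 footnote 4 and the rest of 7.5 say otherwise. The defect is conflicting wording.
- *That the substituted grade is the treating operator's.* The SAP says investigator-reported; 6.9 does not say who assigns the one-year grade.
- *That the bias is upward.* This is plausible, but the documents report no site-versus-core-lab difference. The protocol's bibliography lists a study of such differences by title only.

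It is also fair to say that core-lab-only analysis does not remove selection: if images are missing selectively, the patients with reads are a selected group. That is why the fix needs a site-substituted sensitivity analysis too.

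**Conclusion.** The concern holds as a gap in the analysis rules. As written, the SAP lets site-only grades into the primary and secondary Raymond-Roy endpoints, reports no count of them, plans no analysis that excludes them, and leaves them outside the Section 12 sensitivity analyses. Protocol 6.7 and 6.9 point to a different intention, and the upload wording is inconsistent.

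The effect on the result is unknown. Under the assumed ranges (10-30% site-only, 5-10 points difference) the shift would be 0.5 to 3.0 points against a half-width of 2.28. Only the upper end exceeds the half-width, and if site-only reads are few the effect is small. This should be settled before database lock, because the choice of reader should not be made with the grades in view.

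**What to change.** **SAP 8.1 and 8.2**

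- Base the Raymond-Roy occlusion endpoints on core-lab reads only. Leave the retreatment rate out of this rule, since it comes from site-collected retreatment information.
- Keep retreated patients as Class III, or as recanalization for that endpoint, whether or not a core-lab read exists. Without this, a retreated patient lacking a read would turn from a failure into a missing value, which would raise the observed rate.
- Treat all other patients without a core-lab read as missing under Section 12.
- For recanalization or progressive thrombosis, require core-lab reads at both time points, apart from retreated patients.
- Report the number of patients with a site read only, at each time point.

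**SAP Section 12.** Add a sensitivity analysis that uses the core-lab read where present and the site read otherwise. Compared with the core-lab-only result, it also addresses selective image submission.

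**Protocol 7.5.** Change 'may be' to 'will be', to agree with 6.7 and 6.9.

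**Cost.** Wording changes in both documents, and somewhat fewer evaluable patients. The half-width would be about 2.56 points at 576 reads and 2.7 at 504, both inside the stated ±3%. The worst-case and best-case bounds would widen, because they would then include the patients without an independent read.

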8.2 Secondary Effectiveness Analysis

For the secondary effectiveness endpoints, frequency counts, percentages, and two-sided 95% Wald confidence intervals will be reported using the ITT population:

- **Immediate post-procedure occlusion rate:** The percentage distribution of patients assessed as each of Raymond-Roy Class I, Class II, and Class III out of patients who had a Raymond-Roy evaluation done (Class I, II, or III) at immediate post-procedure.
- **Retreatment rate at final follow-up:** The percentage of patients who had the target aneurysm retreated since the index procedure out of patients who have data on this question (Retreatment, No Retreatment) at the time of final follow-up. Staged procedures are not retreatments for the purposes of running all SURF study analyses.
- **Aneurysm Occlusion Raymond I post treatment:** The percentage of patients assessed as Raymond-Roy Class I out of patients who had a Raymond-Roy evaluation done (Class I, II, or III) at immediate post-procedure.
- **Aneurysm Occlusion Raymond I at final follow-up:** The percentage of patients assessed as Raymond-Roy Class I out of patients who had a Raymond-Roy evaluation done (Class I, II, or III) at the time of final follow-up. Retreatments at final follow-up will be modelled as Raymond-Roy Class III.
- **Aneurysm recanalization or progressive thrombosis from post procedure to final follow-up:** The percentage of patients who experienced a deterioration in Raymond-Roy Occlusion Grading (aneurysm recanalization; Class I becoming II or III, or Class II becoming III) or improvement in Raymond-Roy occlusion (progressive thrombosis; Class II becoming I, or Class III becoming I or II) out of patients who had a Raymond-Roy evaluation done at both time points. Retreatments at final follow-up will be modelled as aneurysm recanalization.

The effectiveness endpoints will be reported using only the Raymond-Roy Occlusion Grading Scale. However, frequency counts, percentages, and two-sided 95% Wald confidence intervals will also be provided for the Meyers Consensus Grading Scale Grades 0, 1, 2, 3, 4, and 5 at immediate post-procedure and final follow-up, using the ITT population and core lab data.

Aneurysm packing densities will be reported as the coil volume of all Penumbra and non-Penumbra coils implanted divided by the aneurysm volume as measured by the core lab, based on two-dimensional geometric modeling as the primary analysis and the ABC method as a supplemental analysis.

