16.4.8 Recanalization

Defined as an increase in size of the remnant in contrast filling of the aneurysm sac using results of immediate post-stent/embolization angiography as baseline.

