Approximately 800 patients will enroll in this post-market study, resulting in 720 patients who achieve final follow-up after 10% anticipated attrition. This sample size provides adequate precision to estimate the primary effectiveness and safety endpoints.

Primary Endpoint	Assumption for Observed Rate ^[1]	95% CI ^[2]	Precision
Adequate occlusion defined as Raymond-Roy Occlusion Class I and II at final follow-up	89% (320/360)	86% to 92%	Greater than $\pm 3.5\%$
	89% (401/450)	86% to 92%	Greater than $\pm 3\%$
	89% (481/540)	86% to 92%	Greater than $\pm 3\%$
	89% (561/630)	87% to 91%	Greater than $\pm 3\%$
	89% (641/720)	87% to 91%	Greater than $\pm 3\%$
Device-related SAE up to 7 days or discharge	2.8% (11/400)	1.1% to 4.4%	Greater than $\pm 2\%$
	2.8% (14/500)	1.4% to 4.2%	Greater than $\pm 1.5\%$
	2.8% (17/600)	1.5% to 4.2%	Greater than $\pm 1.5\%$
	2.9% (20/700)	1.6% to 4.1%	Greater than $\pm 1.5\%$
	2.8% (22/800)	1.6% to 3.9%	Greater than $\pm 1.5\%$
SAEs within 24 hours post-procedure	9.0% (36/400)	6.2% to 11.8%	Greater than $\pm 3\%$
	9.0% (45/500)	6.5% to 11.5%	Greater than $\pm 2.5\%$
	8.8% (53/600)	6.6% to 11.1%	Greater than $\pm 2.5\%$
	8.9% (62/700)	6.8% to 11.0%	Greater than $\pm 2.5\%$
	8.9% (71/800)	6.9% to 10.9%	Greater than $\pm 2.5\%$

^[1] Set at SMART CLP 10023 Registry interim observed results (data on file at sponsor)

^[2] Two-sided 95% Wald normal approximation binomial proportion confidence interval

3 Interim Analysis

As there will be no interim analyses for the purpose of terminating the study early for success or futility, alpha adjustments will not be made to the confidence intervals in the final analysis. However, interim analysis may be performed for the purpose of publication or regulatory submission of SURF results.

4 Analysis Populations

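### The change endpoint counts occlusion gained at a staged second procedure as progressive thrombosis, and no planned analysis separates staged patients

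*Combined protocol and SAP*

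**What the plan says.** The SAP treats a second intervention on the target aneurysm as a failure of the first. For the primary endpoint (SAP 8.1), "Retreatments at final follow-up will be modelled as Raymond-Roy Class III"; SAP 8.2 applies the same rule to Raymond I at follow-up. For the change endpoint, "Retreatments at final follow-up will be modelled as aneurysm recanalization". The retreatment endpoint is "The percentage of patients who had the target aneurysm retreated since the index procedure", among patients with data on the question.

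One sentence in the retreatment definition then removes a group from all of this: "Staged procedures are not retreatments for the purposes of running all SURF study analyses". The word staged appears nowhere else in either document. Protocol 16.4 defines neither staged procedure nor retreatment.

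The favourable half of the change endpoint (SAP 8.2) is "improvement in Raymond-Roy occlusion (progressive thrombosis; Class II becoming I, or Class III becoming I or II", among patients graded at both time points. It says nothing about procedures in between.

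On the starting image:
- Protocol 6.2 makes the procedure day 0 and lists one procedure visit.
- Table 2 schedules occlusion grading at the procedure and at final follow-up only. Protocol 7.5 and 11.1 name the same two images for the core lab.
- Table 2, footnote 5, adds that "Occlusion Grading and other datapoints will be collected if retreatment occurs prior to study exit". It does not mention staged procedures.
- Protocol 16.4.8 defines recanalization "using results of immediate post-stent/embolization angiography as baseline" and does not say which stage is meant.

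**The concern.** The retreatment rule keeps occlusion achieved by a later intervention from being read as the result of the index coiling. The staged exemption lifts that protection in every analysis and puts nothing in its place.

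The clearest harm is in the change endpoint. Progressive thrombosis is a claim about what the aneurysm does after coiling without further help. If the starting grade precedes a planned second stage and the final grade follows it, the difference includes the effect of the second procedure, and the label is wrong for that patient even when staging was entirely proper.

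The second harm is loss of transparency. Adequate occlusion and Raymond I at one year mix patients treated once with patients treated in stages. The 75% SMART and final-WAVE criteria (Protocol 5.1) are settled when the index procedure is complete (Protocol 6.4), and nothing limits or separately reports the devices used at a second stage. A reader of the results could not tell how much of the one-year rate belongs to the index coiling.

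**Working it through.** **Applying the rules to one patient.** Take a patient graded Class III after day 0, given a planned second stage, and graded Class I at one year.

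| Endpoint | Rule | Score |
|---|---|---|
| Retreatment | staged is not retreatment | no |
| Primary, Class I/II | observed grade | success |
| Raymond I at follow-up | observed grade | success |
| Change, starting at the day-0 image | III to I | progressive thrombosis |
| Change, starting after the last stage | depends on that grade | not fixed by the plan |

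The fourth row follows from the schedule, which provides no other starting image. The fifth would remove the error, but no text calls for it.

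**Is the group visible elsewhere?** SAP 7 (disposition) does not count staged patients, SAP 9 (subgroups) does not list them, and the sensitivity analyses in SAP 12 concern missing data only.

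**The plan's own figure.** SAP Section 2 has 800 patients, "resulting in 720 patients who achieve final follow-up after 10% anticipated attrition", and assumes 641/720 with a Wald interval.
- p = 641/720 = 89.03%
- Half-width = 1.96 × √(0.8903 × 0.1097 / 720) = 2.28 points
- Interval = 86.74% to 91.31%, matching the stated 87% to 91%

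**Weight of one patient.** 1/720 = 0.14 points of the primary rate. The change endpoint has at most 720 patients if no more than 720 have a final grade, so one misclassified patient is worth at least 0.14 points there.

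**Assumed staged shares.** The documents give no staged rate. The shares below are assumptions, and every staged patient is taken to be Class I/II at follow-up.

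| Share of 720 | Patients | Primary if scored Class III (95% CI) | Primary if excluded |
|---|---|---|---|
| 1% | 7 | 634/720 = 88.1% (85.7 to 90.4) | 634/713 = 88.9% |
| 2% | 14 | 627/720 = 87.1% (84.6 to 89.5) | 627/706 = 88.8% |
| 5% | 36 | 605/720 = 84.0% (81.4 to 86.7) | 605/684 = 88.5% |

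If all these patients also improved in class, progressive thrombosis would contain 7/720 = 1.0, 14/720 = 1.9 or 36/720 = 5.0 points produced by a procedure.

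**Retreatment rate.** The prior registry figure in Protocol Section 1 is 6/157 = 3.8%, or about 28 of 720 (3.9%). Adding 7, 14 or 36 gives 35/720 = 4.9%, 42/720 = 5.8% or 64/720 = 8.9%.

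**The case against.** The best reply is that a planned second stage belongs to one course of treatment. Scoring it as a failure would be wrong, so the exemption is sound for the primary and retreatment endpoints. That stands. It means the Class III column above does not measure bias in the primary rate; it shows what the most severe rescoring would do.

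A second reply is that the SAP says post procedure, not post index, and Protocol 16.4.8 leaves the stage open, so the starting image could be the one after the last stage. The wording does allow this. But only one procedure visit and one post-procedure image are scheduled, and the extra grading in footnote 5 is tied to retreatment, which staged procedures are declared not to be. An analyst following the schedule would use the day-0 grade.

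Third, the effect is not all in one direction. Index treatment left incomplete by plan lowers immediate post-procedure occlusion and Raymond I post treatment. That is also true, and it is another reason to show these patients separately.

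A reader might go further and infer that operators can call an unplanned rescue procedure staged after seeing a poor result. The documents do not support that. They do not say who assigns the label or when, and in ordinary use staged means planned. The CRFs and Core Lab Charter, which might settle it, are not among the documents. The missing definition is a gap to close, not evidence of relabelling.

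**Conclusion.** The point holds for the change endpoint as a wrong result from a stated rule: with the scheduled starting image, improvement produced by a staged procedure is counted as progressive thrombosis. For the primary, Raymond I and retreatment endpoints it is a failure of separation: staged and index-only patients are pooled and nothing planned shows the effect.

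The size is unknown. Each patient is worth 0.14 points on the planned 720. The 88.1%, 87.1% and 84.0% figures assume a staged share, assume every such patient is Class I/II, and score all of them as failures. It would be a mistake to read them as the amount by which the primary rate is inflated. The 5% case is larger than the whole 3.8% retreatment benchmark and has no source in the documents. If staged patients are left out instead, the rate moves by about half a point at most over the same range.

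The study is single-arm and descriptive, with no success threshold, so no pass or fail conclusion turns on this. It is still worth correcting, because the affected rates will be reported as device performance.

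**What to change.** Revise SAP 8.2 before database lock, as SAP 13 allows:

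1. **Starting grade.** For recanalization/progressive thrombosis, staged patients start from the grade after their last planned stage. Where no such image was collected, leave them out of this endpoint and report how many.
2. **Reporting and sensitivity.** Give the number of staged patients and the devices used at later stages. Repeat the primary, Raymond I at follow-up and retreatment endpoints with staged procedures scored as retreatments, labelled as a sensitivity analysis. The primary analysis keeps the exemption.
3. **Definition.** Count a procedure as staged only if dated source records or the CRF show that it was planned at or before the index procedure; otherwise it is a retreatment. Accepting source records matters: relying on a new CRF item alone would score genuine staged patients enrolled before its introduction as failures.

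The cost is a few sentences of SAP text, a check of source records for patients with a second procedure, retrieval of the later-stage image where it exists, and one extra row for each of three endpoints. Some reported rates may be slightly less favourable.

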4.2.2 Secondary Endpoints

Efficacy:

- Immediate post-procedure occlusion rates
- Retreatment rate at final follow-up
- Aneurysm Occlusion Raymond I post treatment
- Aneurysm Occlusion Raymond I at final follow-up
- Aneurysm recanalization or progressive thrombosis from post procedure to final follow-up

Safety:

- Major ipsilateral stroke
- Device related SAE at final follow-up
- All-cause morbidity and mortality

5. Study Population

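### SAP 8.2 words recanalization and progressive thrombosis as one percentage, adding worsening to improvement, and its recanalization rule does not match protocol 16.4.8

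*Combined protocol and SAP*

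**What the plan says.** Protocol 4.2.2 lists as a single secondary endpoint "Aneurysm recanalization or progressive thrombosis from post procedure to final follow-up". SAP 8.2 turns it into one percentage. The numerator takes a deterioration, spelled out as "aneurysm recanalization; Class I becoming II or III, or Class II becoming III", and continues "or improvement in Raymond-Roy occlusion (progressive thrombosis; Class II becoming I, or Class III becoming I or II". The denominator is patients graded twice, "out of patients who had a Raymond-Roy evaluation done at both time points", with no restriction by starting class.

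A rule on retreated patients follows: "Retreatments at final follow-up will be modelled as aneurysm recanalization". Elsewhere in SAP 8.2, staged procedures are excluded from what counts as a retreatment. For every secondary effectiveness endpoint, "frequency counts, percentages, and two-sided 95% Wald confidence intervals will be reported using the ITT population".

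Protocol 16.4.8 has its own definition of recanalization: "an increase in size of the remnant in contrast filling of the aneurysm sac", with the immediate post-embolization angiogram as baseline. SAP 8.2 neither cites nor reconciles it. Protocol 16.4 has no entry for progressive thrombosis.

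**The concern.** There are three separate difficulties.

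- **Opposite outcomes in one figure.** Taken literally, the endpoint is the share of patients whose class changed in either direction. A high value could mean that many aneurysms reopened or that many residuals closed. SAP 9 and SAP 11 carry the secondary endpoints into every subgroup and site table, so the ambiguity would be repeated there.
- **Two definitions of recanalization.** The protocol asks whether the remnant grew; the SAP asks whether the class changed. The same patient can be recanalized under one and not under the other.
- **Retreatment of an index residual.** A patient left at Class III and later retreated is counted as recanalized even if nothing reopened.

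At stake is whether a reader can interpret the only listed endpoint that measures change in occlusion between the procedure and follow-up.

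**Working it through.** **1. Interval method and N.** SAP 2 plans 800 patients, "resulting in 720 patients who achieve final follow-up after 10% anticipated attrition": 800 × (1 − 0.10) = 720. The Wald interval is p ± 1.96 × √(p(1 − p)/n). For the primary occlusion rate, 641/720 = 89.03%, half-width 2.28 points, interval 86.74% to 91.31%. This reproduces the SAP's 87% to 91%. The documents give no rate, N or precision for the recanalization and thrombosis endpoint. I use 720 as the most patients who could have both grades.

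**2. One percentage for two directions.** The counts are assumed, for illustration only.

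| Recanalized | Thrombosed | Combined, as worded |
|---|---|---|
| 72/720 = 10.0% (7.8 to 12.2) | 180/720 = 25.0% (21.8 to 28.2) | 252/720 = 35.0% (31.5 to 38.5) |
| 180/720 = 25.0% (21.8 to 28.2) | 72/720 = 10.0% (7.8 to 12.2) | 252/720 = 35.0% (31.5 to 38.5) |
| 36/720 = 5.0% | 216/720 = 30.0% | 252/720 = 35.0% |
| 216/720 = 30.0% | 36/720 = 5.0% | 252/720 = 35.0% |

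Four quite different results give the same estimate and the same interval.

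**3. The definitions side by side.** For its two follow-up occlusion endpoints (SAP 8.1 and 8.2), the SAP treats a retreated patient as Class III. I carry that convention over here to compare the rules.

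| Patient | SAP class rule | SAP retreatment rule | Protocol 16.4.8 |
|---|---|---|---|
| II to II or III to III, remnant larger, not retreated | No change | Does not apply | Recanalized |
| Starts I or II, retreated (taken as III) | Deteriorated | Recanalized | Only if the remnant grew |
| Starts III, retreated (taken as III), remnant not larger | No change | Recanalized | Not recanalized |

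The SAP and the protocol disagree in both directions. Within the SAP, the class and retreatment rules conflict only for patients who start at Class III.

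**4. How common a Class III start is.** From the studies summarised in protocol section 1: registry interim (444 − 354)/444 = 90/444 = 20.3%; the 59-patient review 28.8% (its third figure carries no label and is taken as Class III); the 34-aneurysm cohort 35% + 15% = 50%. This group is not negligible, so starting class should be visible in the tables.

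**5. Retreated patients in the denominator.** The denominator requires two grades, while the retreatment rule assigns an outcome whether or not there is a follow-up grade. A footnote to protocol Table 2 has occlusion grading collected when retreatment occurs before study exit, but SAP 8.2 does not say whether that grade serves as the follow-up grade.

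**The case against.** The strongest reply is that two rates are the natural reading. Each component is named with its own class moves. Retreatments are assigned specifically to recanalization, which has a purpose only if the components are kept apart. SAP 5 summarises categorical variables by category. This is a fair account of the likely intent, but no sentence commits to it. The first bullet of SAP 8.2 asks explicitly for a percentage for each class; this bullet does not.

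It can also be said that counting retreatment as unfavourable is conservative, that retreatment is reported as its own endpoint, and that Meyers grades at both time points show finer detail. All true. But the Meyers results are planned as distributions, not patient-level change, and a conservative choice still needs a label that matches what happened.

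A reader might infer more than the documents support:

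- **That the all-pairs denominator dilutes the recanalization rate by a known amount.** The issue arises only once the two directions are split. A Class III starter can be an event through the retreatment rule and, under 16.4.8, through growth. The class mix among paired patients is unknown: the registry graded 444 patients after the procedure but only 140 at one year. All pairs is a usable denominator if labelled.
- **That a combined figure would be mostly improvement.** In the 34-aneurysm cohort, Class I rose from 24% to 62%, so at least 38% improved; on class shares at most 24% + 12% = 36% worsened. But its 14.7% retreatment rate, counted as recanalization, could move up to 14.7 points. The cohort is also small and used a modified scale.
- **That this is the study's principal durability measure.** Occlusion at final follow-up is primary, and this is the last of five secondary effectiveness endpoints.
- **That remnant growth must now be measured.** Protocol 11.1 commits the core lab to occlusion grading as a minimum, 16.4.8 sets no growth threshold, and follow-up may be by DSA, CTA or MRA.

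**Conclusion.** Wrong as written, with limited impact. Followed literally, SAP 8.2 yields a percentage that cannot be interpreted: 35.0% is compatible with 5% recanalized and 30% thrombosed, or with the reverse. Those counts are assumptions, but the conclusion does not depend on them, because any split of the same total prints the same figure. It rests on the literal wording; if two rates were intended, one sentence settles that part.

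The mismatch with protocol 16.4.8 and the treatment of retreated Class III starters hold under either reading. Their size in SURF cannot be estimated from the documents. The endpoint is secondary and descriptive, with no test or sample size attached, so neither the primary result nor the planned precision is affected.

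**What to change.** Amend SAP 8.2 before the sign-off that the SAP places ahead of database lock:

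1. Report recanalization (class deterioration) and progressive thrombosis (class improvement) as two rates, each with its own 95% interval, over all paired patients.
2. Add a 3×3 table of post-procedure class by follow-up class, so that rates among patients able to worsen (starting Class I or II) or to improve (starting Class II or III) can be read off.
3. Show retreatments of a Class III index residual on a separate line from other recanalization.
4. State whether retreated patients without a follow-up grade enter the denominator.
5. Reconcile SAP 8.2 with protocol 16.4.8, for example by stating that the endpoint is class-based and that growth within a class is not counted.

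The cost is SAP wording and a few table rows. The core lab already grades both time points, and no new remnant measurements are required.
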